### 8.1.2. Analyses of Other Secondary Efficacy Endpoints

Other secondary endpoints to be assessed include:

- Change and percent change from baseline in IOP at each timepoint/post-baseline visit
- Change and percent change from baseline in mean diurnal IOP at each post-baseline visit
- Having a mean diurnal IOP reduction  $\geq 20\%$ ,  $\geq 25\%$ , or  $\geq 30\%$  from Baseline (Visit 2) at each post-baseline visit
- Having a mean diurnal IOP  $\leq 18\text{mmHg}$  at each post-baseline visit

For continuous secondary endpoints (change and percent change from baseline in IOP/mean diurnal IOP) at Week 1 (Visit 3), Week 6 (Visit 4), and Month 3 (Visit 5), both an analysis using a MMRM will be performed and descriptive summaries will be generated. The MMRM will be analogous to the MMRM used in the analysis of the primary endpoint. For both the analysis using MMRM and descriptive summaries of the IOP or mean diurnal IOP (raw) scores, IOP values obtained after using rescue therapy will be censored (i.e., treated as missing).

For the following binary secondary endpoints, the responder rates will be analyzed using the Pearson's chi-square test for a  $2\times 2$  contingency table; differences between the DE-117 and Timolol arms will be reported along with corresponding p-values:

- Having a mean diurnal IOP reduction  $\geq 20\%$ ,  $\geq 25\%$ , or  $\geq 30\%$  from Baseline (Visit 2) at each post-baseline visit
- Having a mean diurnal IOP  $\leq 18\text{mmHg}$  at each post-baseline visit

The above secondary efficacy endpoint analyses will be repeated on pediatric subjects.

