14.7.2.2. Other Secondary Efficacy Endpoints

Other secondary endpoints to be assessed include:

- Change and percent change from baseline in IOP at each timepoint/post-baseline visit
- Change and percent change from baseline in mean diurnal IOP at each post-baseline visit
- Having a mean diurnal IOP reduction $\geq 20\%$, $\geq 25\%$, or $\geq 30\%$ from Baseline (Visit 2) at each post-baseline visit
- Having a mean diurnal IOP ≤ 18 mmHg at each post-baseline visit

The Continuous secondary endpoints will be analyzed using MMRM on observed cases. More details on the model specifications will be provided in the SAP.

The binary secondary endpoints will be analyzed using the Pearson's chi-square test for a 2×2 contingency table. The Fisher's Exact test may be conducted as a sensitivity analysis.

Subgroup analyses may be performed for secondary endpoints using descriptive statistics.

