**Figure 1: Study Design Diagram**

#### 3.2. Randomization and Masking

A blocked randomization stratified by age (< 18 and  $\geq$  18 years old) will be employed to randomize eligible subjects in a 1:1 ratio to receive either DE-117 or Timolol. The randomization schedule will be generated and implemented by an independent CRO, Medidata Solutions, Inc. (New York City, NY).

During the 3-month double-masked treatment period, the subjects, Investigators, Examiners, and Santen personnel involved in the conduct of the study will be masked to the study treatment. An authorized unmasked study staff member who is not the Investigator or Examiner at the investigative site will dispense and collect study medication(s) and will query about dosing compliance. In case of a medical emergency, when the unmasking of a subject's treatment assignment code becomes necessary for the welfare of that subject, the Clinical Investigator may reveal the treatment information by unmasking which treatment the subject has received through the study's interactive web response system (Medidata RTSM).

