## 4.3. Efficacy-Related Definitions

### 4.3.1. Response Endpoint and Response Rate

Four IOP response endpoints ([Table 5](#)) will be evaluated at each post-Baseline visit during the double masked-period (Week 1, Week 6, or Month 3) and open-label period (Month 6, Month 9, and Month 12) in this study:

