## 6. GENERAL CONSIDERATIONS

All measures will be summarized by treatment (planned or actual received) descriptively. Continuous variables will be summarized using descriptive statistics such as number of observations (n), mean, standard deviation, median, minimum, and maximum. Categorical variables will be tabulated using frequency (n) and percent (%).

The statistical testing will be conducted at a significance level of 0.05 (two-sided) and the 95% confidence interval will be shown, unless specified otherwise. No statistical testing will be conducted for safety measures.

All data manipulations, descriptive summaries, and statistical hypothesis testing will be performed using Statistical Analysis System (SAS) Version 9.4 or later.

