### 6.1. Adjustments for Covariates

In general, the inferential analysis of each IOP endpoint will adjust for the baseline IOP. Detailed information on covariate adjustment is provided in [Section 8.1](#).

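### SAP 8.1.2 tests the IOP responder endpoints without baseline adjustment, an unexplained exception to SAP 6.1 that matters mainly for the 18 mmHg endpoint

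*SAP*

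**What the plan says.** SAP 4.3.1 defines four responder endpoints on mean diurnal IOP: reductions of at least 20%, 25% and 30% from baseline, and a value of 18 mmHg or lower. For all four, SAP 8.1.2 specifies: "For the following binary secondary endpoints, the responder rates will be analyzed using the Pearson's chi-square test". On reporting it adds that "differences between the DE-117 and Timolol arms will be reported along with corresponding p-values". Protocol 14.7.2.2 names the same method, with Fisher's exact test as an optional sensitivity analysis: "The binary secondary endpoints will be analyzed using the Pearson's chi-square test for a 2×2 contingency table".

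SAP 6.1 says: "In general, the inferential analysis of each IOP endpoint will adjust for the baseline IOP". Its next sentence begins "Detailed information on covariate adjustment is provided in" and points to Section 8.1, which contains 8.1.2. The continuous secondary endpoints in 8.1.2 use an MMRM analogous to the primary one, which has baseline IOP as a covariate. SAP 6 sets a default for statistical testing: "the 95% confidence interval will be shown, unless specified otherwise".

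Under SAP 3.2, randomization is stratified by age group only. SAP 6.4 limits the fixed sequence to seven tests on the primary and key secondary endpoints, so the responder endpoints are outside it.

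**The concern.** Adult eyes qualify with IOP between 22 and 34 mmHg (Protocol 8.1), while the 18 mmHg cut is fixed. An eye starting at 22 mmHg needs a fall of 4/22 = 18%; one starting at 33 mmHg needs 15/33 = 45%. Baseline can therefore predict response strongly, and an unadjusted 2×2 comparison discards that information. Two things follow for this endpoint: lower power than an adjusted analysis of the same data, and a rate difference that moves with any chance imbalance in baseline IOP.

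The sponsor treats baseline IOP as important elsewhere. It is a covariate in every MMRM, and a cut at 25 mmHg defines both a key secondary endpoint and a subgroup. Section 8.1, where 6.1 places the covariate detail, says nothing about why responders are treated differently.

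**Working it through.** **The plan's own figure.** No power or response rate is stated for any responder endpoint. The 90% in SAP 3.3 concerns non-inferiority on continuous IOP (margin 1.5 mmHg, SD 4.0 mmHg, correlation 0.6, difference 0, 200 per arm). Requiring three measurements correlated at 0.6 all to have an upper limit of 1.5 mmHg or less gives 91.6% by simulation, close to 90%. The documents do not say which calculation was used, and the figure does not bear on responders.

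**Inputs from the documents.** 200 per arm; SD 4.0 mmHg and correlation 0.6 among repeated measures (SAP 3.3); adult baseline 22 to 34 mmHg (Protocol 8.1).

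**Assumed inputs, not in the documents.** Baseline normal with location 25.5 and SD parameter 2.5, truncated to 22–34 (resulting mean 25.9, SD 2.15); timolol follow-up mean 19 mmHg; effect −1.0 mmHg; baseline/follow-up correlation 0.3 to 0.6. The 0.6 in SAP 3.3 is given for repeated measures and is not stated to hold between washed-out baseline and treated values, hence the range.

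**Follow-up diurnal SD.** 4.0 × √((1 + 2 × 0.6)/3) = 3.43 mmHg.

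**Chi-square power for 18 mmHg or lower, by hand.**
- Response rates: timolol Φ((18 − 19)/3.43) = 0.385; DE-117 Φ(0) = 0.500; difference 0.115.
- Null SE: √(0.4425 × 0.5575 × 2/200) = 0.0497. Alternative SE: √((0.385 × 0.615 + 0.25)/200) = 0.0493.
- Power: Φ((0.115 − 1.96 × 0.0497)/0.0493) = Φ(0.36) = 64%.

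**Simulated power (1,500 to 3,000 runs), chi-square → logistic regression with baseline mean diurnal IOP.**

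| Correlation | ≤18 mmHg | ≥20% | ≥25% | ≥30% |
|---|---|---|---|---|
| 0.3 | 63% → 65% | change under 1 point | change under 1 point | change under 1 point |
| 0.45 | 63.2% → 70.4% | 65.3% → 65.1% | 72.5% → 72.9% | 73.9% → 73.8% |
| 0.6 | 65.1% → 75.2% | 73.9% → 73.3% | 81.6% → 82.3% | 81.6% → 82.8% |

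A separate simulation at 200 per arm and a 1.0 mmHg effect gave, for 18 mmHg, 65% → 69%, 64% → 70% and 65% → 74% at the same three correlations. Over a wider range (correlation 0 to 0.6, baseline SD parameter 1.5 to 4.0) the gain was about 0 to 13 points for 18 mmHg and about 0 to 5 points for the percent endpoints. With no treatment effect, both tests rejected in about 5% of runs (4.1% to 5.6%).

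**Why the percent endpoints differ.** Their cut on follow-up IOP is 0.80, 0.75 or 0.70 times baseline, so it already moves with baseline. At correlation 0.45 the slope of follow-up on baseline is 0.45 × 3.43/2.15 = 0.72, close to those multiples, and little baseline dependence is left to adjust for.

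**Chance imbalance, no treatment effect.**
- SE of the baseline difference: 2.15 × √(2/200) = 0.215 mmHg. Two SE: 0.43 mmHg, taken with DE-117 lower.
- Shift in follow-up mean: (0.3 × 3.43/2.15) × 0.43 = 0.21 mmHg at correlation 0.3; 0.41 mmHg at 0.6.
- Density at the 18 mmHg cut: 0.382/3.43 = 0.111 per mmHg. The shift in rate difference is then about 2.3 and 4.6 points; simulation gives 2.3 and 4.8.
- Chi-square rejection rate given that imbalance: 6.3% and 12.9%, against 4.6% and 5.0% with adjustment. At an imbalance of 0.22 mmHg (about one SE) it was 4.8% and 4.9%.
- Percent endpoints at two SE: shift of at most 1.7 points; rejection rate 4.7% to 6.6%.

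**The case against.** The chi-square is a valid test in a randomized trial. Its overall type I error is about 5%, and only the error conditional on a sizeable imbalance moves. The protocol prespecified it. Non-inferiority is judged on continuous IOP with baseline-adjusted MMRMs and 95% CIs, so the main question does not depend on these endpoints, and no power was claimed for them. All of this stands and sets the priority.

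Four stronger readings may tempt a reader, and the documents do not support them.
- *The SAP breaches its own covariate rule.* SAP 6.1 is qualified by its opening words and defers to Section 8.1, where the chi-square is specified. This is an unexplained exception, not a breach.
- *Only p-values are reported, with no interval.* SAP 8.1.2 also reports the between-arm differences, and SAP 6 shows 95% CIs by default. What is missing is a named interval method for a difference in rates.
- *All four endpoints lose power.* In the main scenarios three of them barely change.
- *The test inflates false positives.* Unconditionally it does not.

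A practical objection also stands in part. SAP 8.1.2 repeats these analyses in pediatric subjects, at most 30 in total, where a logistic model with a covariate may fail to fit. That limits the remedy to adults.

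**Conclusion.** The point holds in limited form. All four responder endpoints are tested without baseline adjustment, no reason is given, and baseline IOP is not balanced by stratification. The cost falls mainly on the 18 mmHg endpoint: about 2 to 10 points of power at baseline/follow-up correlations of 0.3 to 0.6, and a rate difference that shifts by about 2 to 5 points under a two-SE baseline imbalance. For the percent-reduction endpoints the power change is about 0 to 1 point in those scenarios.

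These sizes depend on a baseline distribution, timolol mean, effect and baseline correlation that the documents do not give. At zero correlation the 18 mmHg gain disappears. Priority is low: the endpoints are outside the multiplicity-controlled sequence and the primary conclusion is unaffected.

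**What to change.** Before unmasking, amend SAP 8.1.2:
- For adults, analyze attainment of 18 mmHg or lower at each double-masked visit by logistic regression on treatment and baseline mean diurnal IOP. Extending this to all four endpoints for consistency is optional.
- Report the standardized (marginal) difference in response rate with its 95% CI and name the interval method. This keeps the effect measure on the scale of the rate difference already planned.
- Keep the chi-square as supportive.
- For the pediatric subjects, keep the unadjusted test or use an exact one. The FAS is not restricted to adults, so the text should say to whom the model applies.

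Record the departure from the protocol's named test in SAP Section 10. If the sponsor prefers to keep the chi-square as the main analysis, SAP 6.1 should state and justify the exception and 8.1.2 should still name the interval method.

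The cost is SAP wording, slightly more analysis work and a documented departure from the protocol. No new data are needed, since baseline mean diurnal IOP is already a covariate in the diurnal MMRM.

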### **8.1.3. Subgroup Analyses**

The homogeneity of treatment effects among prospectively defined subgroups was assessed using MMRM analyses of IOP (at each visit and timepoint) and mean diurnal IOP (at each visit) for the following subgroups:

- Age ( $< 18$ ,  $\geq 18$  and  $< 65$ , or  $\geq 65$  years)
- Sex (males or females)
- Race (White or Black)
- Primary ocular diagnosis [OAG (including pigmentary glaucoma and pseudoexfoliative glaucoma), OHT, or JOAG]
- Prior use of IOP-lowering medication ( $\beta$ -adrenergic antagonist, prostamide or prostaglandin analogue,  $\alpha$ -adrenergic agonist, carbonic anhydrase inhibitors, or none)
- Mean diurnal IOP at baseline ( $< 25$  or  $\geq 25$  mmHg)
- Lens status (phakic or pseudophakic/aphakic)

Other subgroup analyses may be performed as deemed necessary.

## **8.2. Efficacy Analyses for Open-Label Period**

For efficacy measures during open-label period, no inferential analysis will be performed. Summary statistics will be provided on the following variables for open-label and entire study periods separately for all subjects who entered the open-label treatment period.

- Raw scores, change from baseline, and percent change from baseline in IOP at each timepoint/post-baseline visit
- Raw scores, change from baseline, and percent change from baseline in mean diurnal IOP at each post-baseline visit

## 9. SAFETY ANALYSES

The safety-related measures collected in this study include AEs, best-corrected visual acuity, slit-lamp biomicroscopy (severity scores for 12 parameters), ophthalmoscopy (cup-to-disc ratio, glaucomatous optic nerve severity score, and assessments of retina, macula, choroid, and vitreous), and eyelid sulcus/eyelid/eyelash/iris color. In the event that a subject took both DE-117 and Timolol during double-masked period of the study, the subject will be summarized with those receiving DE-117.

All the safety-related measures will be summarized descriptively by actual treatment received on the Safety population.

### 9.1. Adverse Events

AEs, SAEs, SARs, serious SARs, and significant AEs (AEs leading to study drug discontinuation and AEs leading to death) will be tabulated by type of AEs by treatment arm using actual treatment received for all AEs, ocular AEs, and non-ocular AEs separately.

Besides the overall AE summary, AEs, SAEs, SARs, serious SARs will be tabulated by SOC and preferred term for all AEs, ocular AEs, and non-ocular AEs separately. A subject who experienced multiple AEs within a SOC or preferred term will be counted only once for that SOC or preferred term. Non-serious AEs (including number of events) and ESIs will also be summarized by SOC and preferred term.

All the AE summaries will be performed for double-masked, open-label, and entire study periods separately. For double-masked period summaries, overall AE summary, summary of AE by SOC and PT, SAEs, SARs, and serious SARs will also be tabulated on pediatric subjects separately. For open-label and entire study period summaries, tabulations by treatment received during double-masked period will be provided as well as overall summary for subjects exposed to DE-117. So, for subjects who exposed to the Timolol arm during the double-masked period, their AE summaries under the Overall DE-117 column will be those AEs that started during the open-label treatment period.

AEs, SAEs, SARs, serious SARs, ocular AEs, AEs leading to death, AEs leading to study drug discontinuation, non-TEAEs, and ESIs, if any, will be listed separately.

#### 9.1.1. Ocular Inflammation

Subjects who developed AEs during the study with one of the following preferred terms will be included in the ocular inflammation summary:

- Anterior chamber cell
- Anterior chamber flare
- Eye inflammation
- Anterior chamber inflammation
- Iridocyclitis
- Iritis

- Uveitis

Other preferred terms might be added upon review of the AE data before database lock.

Ocular inflammation leading to study drug discontinuation, requiring steroid treatment, or requiring NSAIDs treatment will be summarized at the subject level by frequency and percentage separately.

Ocular inflammation start time (in terms of study day) and duration of the AE will be summarized at the eye level using mean, standard deviation, median, minimum, and maximum by study eye and fellow eye separately. To allow for the computation of simple descriptive statistics, only subjects who develop ocular inflammation during the study will be used for the ocular inflammation start time summary, and only subjects who develop these AEs during the study and later resolved will be used in the duration of AE analysis.

The aforementioned summaries will be performed at the eye level. All ocular inflammation AEs will be provided in a listing.

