14.2. Final Analysis

An unmasked final analysis will be performed after all subjects completed Month 3. The analysis will evaluate the efficacy and safety of DE-117 Ophthalmic Solution 0.002% once daily compared with Timolol Maleate Ophthalmic Solution 0.5% twice daily.

Another analysis will be performed after all subjects completed Month 12. The analysis will evaluate the long term efficacy and safety of DE-117 Ophthalmic Solution 0.002% once daily.

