### **5.4. Per-Protocol Set**

The Per-Protocol Set (PPS) is a subset of the FAS. It will be the analysis population for sensitivity analyses that will be conducted for the primary and key secondary efficacy endpoint analyses and will be summarized using treatment as randomized. Any subject affected by a significant protocol deviation that might affect the primary efficacy analysis will be excluded from the PPS. The PPS will be identified before the unmasking of treatment assignments.

Before the unmasking of treatment assignment, Santen's study team will review all protocol deviations, identify subjects with any protocol deviation that could affect the efficacy outcome, and determine whether or not to exclude the subject from the PPS.

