## 6.5. Interim Analysis

No interim analysis is planned for this study.

Analysis of the double-masked period data will be conducted when all the randomized subjects complete their Month 3 Visit, data cleaned and frozen. All efficacy and safety data from open-label period at the time of this data cut will also be analyzed and reported. The [011709IN Data Cut Plan](#) details how data collected during open-label period will be cut for this “snapshot”.

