## 7. SUMMARY OF STUDY POPULATION DATA

### 7.1. Subject Disposition

The disposition of ITT population (i.e., all randomized subjects) will be summarized by treatment period (double-masked and open-label) and by planned treatment (for double-masked period) and overall.

For the double-masked period, the summary will include the number and percentage of ITT subjects in the Safety population, FAS, and PPS. The disposition summary will also include the number and percentage of subjects who completed the study drug, subjects who discontinued the study drug prematurely but continued with study participation until the Month 3 Visit and among which who completed or not completed the Month 3 Visit, as well as the number and percentage of subjects who discontinued from the study or discontinued from the study drug prior to Month 3 Visit by the primary discontinuation reason.

For the open-label period, the summary will include the number and percentage of subjects who received any study treatment during open-label period, and subjects who are still on the study at the time of data cut (for reports other than the final clinical study report). The disposition summary will also include the number and percentage of subjects who completed the study drug, and subjects who discontinued from the study prior to Month 12 Visit by the primary discontinuation reason.

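### The ocular-inflammation and cosmetic-change term lists stay open until an undefined database lock, which as written can fall after the Month 3 unmasking

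*SAP*

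**What the plan says.** SAP 9.1.1 (ocular inflammation, seven preferred terms) and SAP 9.1.3 (cosmetic change, eight terms) each end their list with the same sentence: "Other preferred terms might be added upon review of the AE data before database lock". SAP 9.1.2 (macular edema, two terms) has no such sentence.

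On timing, Protocol 14.2 states: "An unmasked final analysis will be performed after all subjects completed Month 3". That analysis covers safety as well as efficacy. A later one follows: "Another analysis will be performed after all subjects completed Month 12". SAP 6.5 describes the state of the data at the first of these: "Analysis of the double-masked period data will be conducted when all the randomized subjects complete their Month 3 Visit, data cleaned and frozen". It adds: "All efficacy and safety data from open-label period at the time of this data cut will also be analyzed and reported". SAP 7.1 plans to count "subjects who are still on the study at the time of data cut", so AE data are still accruing at that point. SAP 9.1 sets the reporting periods: "All the AE summaries will be performed for double-masked, open-label, and entire study periods separately".

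For another data-dependent choice the SAP does tie the decision to the codes. Section 5.4 says: "The PPS will be identified before the unmasking of treatment assignments".

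**The concern.** A grouping of AE terms is an analysis definition. If it can be extended after the arm split is known, the choice of terms can be steered by the result, deliberately or not, and a reader cannot tell whether it was. A masked review before the codes are opened removes the question.

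The SAP applies that protection to the per-protocol set but not to these two lists. Their only stated limit is database lock, and the Month 3 step is described as a freeze rather than a lock. At stake is the credibility of two of the three dedicated AE groupings in SAP 9.1, not the efficacy conclusion.

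**Working it through.** The plan gives no figure to reproduce. The check is one of sequence, plus one subtraction.

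**1. When the codes are used.** Protocol 14.2 and SAP 6.5: once all subjects have completed Month 3 and the data are cleaned and frozen. Adults then have open-label treatment still to come.

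**2. When the lists close.** SAP 9.1.1 and 9.1.3: at database lock, which neither document defines. The other uses of the term are:
- Protocol 12.1.4 has follow-up information on AEs, SAEs and events of special interest entered before lock. That fits a lock at the end of the study.
- SAP 7.4 has the list of significant deviations settled before lock, and those deviations are reported for both the double-masked and the open-label period. That also fits an end-of-study lock.
- SAP 5.4 does not use the term. Where closure before unmasking was intended, the SAP said so directly.

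The end-of-study lock is therefore the more natural reading, though not the only possible one.

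**3. Whether another provision closes the gap.** Protocol 14.3 requires the SAP to be final before unmasking, but the final SAP itself leaves the lists open. SAP Section 1 requires deviations from the SAP to be justified in the study report, but adding a term is permitted by the SAP and so is not a deviation.

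**4. How long the lists could stay open.** Inputs from SAP Table 4: Month 3 is Day 91 (window 84 to 98) and Month 12 is Day 361 (window 351 to 371).
- Nominal: 361 − 91 = 270 days, about 9 months.
- Shortest within windows: 351 − 98 = 253 days.
- Longest within windows: 371 − 84 = 287 days.

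These are visit-to-visit intervals for an adult who completes. The interval is shorter if the last subject to reach Month 3 is pediatric, because pediatric subjects exit there. The documents give neither the time needed to clean the Month 3 data before unmasking nor the date of the final lock.

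**5. Which outputs could change.** SAP 9.1.1 specifies subject-level frequencies and percentages for inflammation that leads to drug discontinuation, needs steroids or needs NSAIDs. It also specifies start time and duration by eye, and a listing. SAP 9.1.3 specifies start time by eye and a listing. Neither section explicitly specifies a by-arm incidence of the whole grouping. SAP Section 6 rules out statistical testing of safety measures.

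**The case against.** The strongest reply is that database lock is undefined and could mean a lock at Month 3, before the codes are opened. SAP 7.4 and SAP 5.4 both have the sponsor's team reviewing all deviations, one before lock and the other before unmasking, so for the double-masked data the two phrases may mark the same moment. SAP 6.5 also refers to a separate data cut plan, which is not among the documents and may settle the matter. This stands as a caution: the text permits post-unmasking additions but does not show that any are intended. If a Month 3 lock was meant, the change below only records it.

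The second reply is that little harm could follow. Terms can be added but not removed, so no listed case can be hidden. All AEs are tabulated by system organ class and preferred term for each period, and listed, so a reader can largely rebuild either grouping with or without a late term. This stands too, and it limits the weight of the point.

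The third reply is that a relevant term may first be recognised during open-label treatment, and that barring it from the double-masked displays could leave randomised-period cases out of the grouping. That is fair. It is a reason to show both versions rather than to forbid the later one.

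**Conclusion.** The point holds as a minor weakness in prespecification. As written, two AE groupings can be widened after the by-arm results are available, for up to about 9 months. This rests on reading database lock as the end-of-study lock, which the documents favour but do not state, and on an adult being last to reach Month 3.

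A reader might infer more, and the documents do not support it:
- **A shift in percentage points.** No case counts are given and no by-arm incidence of either whole grouping is explicitly specified, so any such figure would be invented.
- **Nine months as a minimum.** The in-window range starts at 253 days and can be shorter with a pediatric subject last.
- **A rewritten double-masked table in the final report.** Protocol 14.2 describes the Month 12 analysis as one of long-term efficacy and safety. Nothing says that the double-masked summaries will be re-run with new terms, although nothing prevents it.
- **Involvement of the designated safety signals.** The events of special interest are pregnancy, medication administration errors and macular edema (Protocol 12.1.3, SAP 4.4.1.4), and the macular edema list is closed.

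No hypothesis test, error rate or primary conclusion is affected.

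**What to change.** In SAP 9.1.1 and 9.1.3, replace database lock as the cut-off with completion of a masked review of AE terms before the Month 3 unmasking.

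Add that any term introduced later is marked as post hoc. Where it affects a double-masked or entire-study summary, the version using the prespecified list remains the main display and the expanded version is shown beside it.

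The cost is a short edit in each of two SAP sections, one masked term review before the Month 3 freeze, and possibly an extra table. No endpoint, sample size or study procedure changes.
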